##### **B. Randomization**

We will use the high quality pseudo-random deviate generator in SAS® (SAS Institute, Inc., Cary, North Carolina) to randomize participants to MACRO or SOC in 1:1 ratio with random block sizes chosen from small even numbers. Exact block sizes will be revealed to the rest of the study team at the conclusion of the study to prevent educated guessing. There are some key demographic differences in populations served by the study sites, as described in the Study Settings section. Thus, randomization will be stratified by site to ensure a balance between the treatment groups with respect to site by design rather than chance. To retain maximum degree of flexibility in post-COVID-19 environment, no other stratification criterion will be employed. The statistician will create schedules which link the randomization sequence number and treatment arm and will provide them to the team constructing the data management system. At randomization, a study team member will establish the link between the participant study identifier and randomization sequence number by clicking on a database function. Randomization data will only be visible to the study statistician and intervention delivery personnel. Therefore, all personnel involved in post assessments will be blind to treatment assignment.

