
**Aim 3 Analysis**- We will examine characteristics of patients likely to reap the greatest benefits from MACRO compared to SOC arms and will be accomplished through exploratory subgroup analyses. We will examine subgroups based on baseline AM-PAC CAT Basic Mobility Scale, frailty status, cognitive function, and readiness for change. Specifically, for each subgroup definition considered, we will add subgroup and subgroup  $\times$  intervention group interaction terms to the models used in Aims 1 and 2. If the interaction terms are statistically significant, we will make subgroup-specific between-intervention comparisons.

Our second avenue of exploration would be to delineate characteristics of patients most/least likely to reap benefits from the MACRO intervention. Specifically, we will only use the data from the MACRO arm, and define a meaningful responder as having a 3-month improvement of at least 2.60 points in AM-PAC CAT Basic Mobility Scale. First, we will compare the baseline characteristics of

responders and non-responders using methods described above. Second, we will fit logistic regression models with responder status (yes/no) as the dependent variable, and each of the baseline characteristics, one-at-a-time, as the sole independent variable to identify which factors are likely to be relevant. Third, we will fit a multivariable logistic regression model with all relevant baseline characteristics as independent variables, and a forward selection strategy to potentially identify a parsimonious collection of relevant baseline characteristics predictive of likelihood of benefit. Finally, to better accommodate non-linear associations and interaction effects among baseline characteristics, we will consider a classification tree model or CART.

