#### D. Sample Size and Power.

**Sample Size Justification.** We base our sample size on published data, published statistical methods, and commercially available software (SAS® POWER procedure; SAS Institute, Inc., Cary, North Carolina). Between-subject standard deviation of the baseline to follow-up change in the primary outcome AM-PAC CAT Basic Mobility Scale is approximately 7.97 in rehabilitation outpatients. We consider 2.60 points a minimally clinically important difference based on MDC68. We plan to randomize 187+187=374 participants, anticipating 149+149 completers assuming a conservative 80% retention rate. We can detect a between treatment arm difference of 2.60 points in AM-PAC CAT Basic Mobility Scale with 80% statistical power in a two-tailed test at  $\alpha=0.05$ . This difference is smaller than the actual observed changes previously reported, indicating ample statistical sensitivity. The logistic regression model proposed in Aim 3 requires a minimum of about 5-10 events per variable, and assuming a half in the MACRO group responds, we would be able to fit a multivariable model with at least 15 variables. Thus, we are confident of the adequacy of sample size to address all aims.

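### Aim 3 dichotomises 3-month mobility change, which discards about 36% of the information at the plan's own responder share, and tests moderation by baseline scores only through subgroups whose cuts are not stated

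*Combined protocol and SAP*

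**What the plan says.** The Aim 3 paragraphs of section 9.1 describe two routes, both exploratory.

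- **Two-arm moderation.** "We will examine subgroups based on baseline AM-PAC CAT Basic Mobility Scale, frailty status, cognitive function, and readiness for change". Variables are taken one at a time: "for each subgroup definition considered, we will add subgroup and subgroup"-by-arm interaction terms to the Aim 1 and Aim 2 models. Cut-points and number of groups are not given, and no analysis with a continuous moderator is planned.
- **MACRO arm only.** A responder is a patient whose AM-PAC Basic Mobility score rises by 2.60 points or more at 3 months. Then "we will fit logistic regression models with responder status (yes/no) as the dependent variable", first with single predictors and then with forward selection. A classification tree may follow. The text does not say that the baseline predictors will be categorised.

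The sample size section powers only the main effect. Its argument for Aim 3 is an events-per-variable rule with half of the MACRO arm responding, after which it judges the sample adequate for every aim.

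**The concern.** Baseline AM-PAC is a continuous score and the Short Blessed a numeric one, and 3-month AM-PAC change is continuous too. Cutting such a variable treats patients just either side of the cut as different and all patients on one side as alike. If the underlying relation is smooth, this costs power, and for the moderators the result also depends on a cut that the plan leaves open and that could be chosen after seeing the data. Aim 3 is meant to show which patients gain most. Interaction tests in a trial sized for its main effect are weak already, so avoidable losses raise the chance of missing a real moderator and make any apparent one less stable.

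**Working it through.** **Inputs from the plan.** The SD of change: "Basic Mobility Scale is approximately 7.97 in rehabilitation outpatients". Numbers: "We plan to randomize 187+187=374 participants, anticipating 149+149 completers assuming a conservative 80% retention rate". Allocation is 1:1, two-sided alpha is 0.05, the responder cut is 2.60 points, and half of the MACRO arm is assumed to respond.

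**Assumptions, not in the documents.** Normal scores, linear moderation, the size of the moderator contrast, and the strength of the baseline predictor.

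**1. The plan's own figure.** The claim is "We can detect a between treatment arm difference of 2.60 points in AM-PAC CAT Basic Mobility Scale" with "80% statistical power in a two-tailed test".
- n per arm = 2(1.96 + 0.842)² × 7.97² / 2.60² = 148.
- Power at 149 per arm: 2.60 / (7.97√(2/149)) = 2.816, and Φ(2.816 − 1.96) = 80.4%.
- 149 / 0.80 gives 187 per arm.

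The figure reproduces, but it concerns the main effect only.

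**2. Responder cut.** For small effects, cutting a normal variable with share f on one side keeps φ(z_f)² / [f(1 − f)] of the information.
- f = 50%: 0.3989² / 0.25 = 2/π = 0.637, a loss of 36%.
- f = 37% or 63%: 0.612, a loss of 39%.
- f = 75%: 0.539, a loss of 46%.

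In power terms (MACRO arm, n = 149, 50% responders):
- A predictor worth 1.83 points per SD has correlation 1.83/7.97 = 0.23 with change. Linear: 0.23 × √149 = 2.80, and Φ(2.80 − 1.96) = 80%. Responder model: 2.80 × √0.637 = 2.24, and Φ(2.24 − 1.96) = 61%.
- Simulation (1,500 runs each), linear against logistic: 69% v 51% at correlation 0.20, and 88% v 69% at 0.25.

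**3. Subgroup interaction.** With two equal subgroups the SE of the difference in treatment effect is 7.97 × √(2/74.5 + 2/74.5) = 1.85.
- Power for a 2.60-point difference: 2.60/1.85 = 1.41, giving 29%.
- Smallest difference detectable with 80% power: 2.80 × 1.85 = 5.17 points, about twice the planned main effect.

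Now keep the moderator continuous. The halves of a normal score differ in mean by 1.596 SD, so a 2.60-point contrast is a slope of 2.60/1.596 = 1.63 points per SD. The SE of the slope difference is 2 × 7.97/√298 = 0.923. Then 1.63/0.923 = 1.76 and power is 42%. Simulations of the same setting gave 39-41% continuous against 27% split. For an assumed 4.1-point contrast they gave 78-79% against 56-59%.

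**4. Dependence on the unstated cuts.** Information lost from a normal moderator:

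| Grouping | Loss |
|---|---|
| Two equal groups | 36% |
| 30/70 | 42% |
| 20/80 | 51% |
| Three equal groups | 21% |
| Four equal groups | 14% |
| Five equal groups | 10% |

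The rows for three or more groups assume that the groups are scored by their means.

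**The case against.** There are five fair points on the other side.

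- **The subgroup figure needs an assumed split.** A reader might infer that every Aim 3 moderator analysis loses about a third. The documents do not support that, because they state neither the number of groups nor the cuts. Nor are all four moderators continuous: readiness for change already has five stages, FRAIL is a five-item scale that loses little if its levels are kept, and Short Blessed scores of 13 or more are excluded, so that score is truncated and 2/π cannot be taken for granted. This stands, and it limits the point mainly to baseline AM-PAC and the cognitive score.
- **Linearity is assumed.** If the true moderation is a step at the median, the advantage reverses: a 2.60-point step gives about 29% power split against 20% linear, and a 4.1-point step about 60% against 43%. So it would be wrong to conclude that categorising can never gain anything. A spline check also spends degrees of freedom that the power figures above do not charge for.
- **The 2.60 cut is fixed in advance.** It is the plan's minimally important difference and also defines the number needed to treat. Who reaches a meaningful improvement is a legitimate question. That justifies reporting the percentage, but it does not remove the loss when the binary outcome is used to search for predictors.
- **A linear model in the MACRO arm alone does not show who benefits.** Without SOC patients, either model predicts improvement, not treatment effect. This stands and is carried into the fix.
- **The stakes are modest.** Aim 3 is exploratory, and for a 2.60-point contrast continuous modelling lifts power only from 29% to 42%. The analysis stays weak.

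**Conclusion.** The point holds as a low-cost improvement to an exploratory aim. The firm part is the responder model: the dichotomy is explicit, and at the plan's own 50% responder share it discards about 36% of the information, or about 60% power where a linear model would have 80% for an assumed predictor worth 1.83 points per SD. The moderator part is conditional: about 36% is lost if baseline AM-PAC or the cognitive score is roughly normal, split at the median and moderates linearly, with about 10% to 51% across other groupings. All power figures use the unadjusted SD of 7.97. Baseline adjustment would raise them somewhat, but the plan gives no correlation. A reader might go further and take this as a flaw in the primary analysis, or expect continuous modelling to make Aim 3 adequately powered. Neither follows: the primary test is untouched, and interaction power remains low for contrasts near 2.60 points.

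**What to change.** **Two-arm models.** Test baseline AM-PAC and the Short Blessed as continuous score-by-arm interactions at 3 months, and FRAIL as an ordinal score, each with a linearity or spline check. The Aim 1 model already carries the baseline value of its outcome as a covariate, so for AM-PAC this adds only products with existing terms. Show the MACRO minus SOC difference with its confidence interval at the 25th, 50th and 75th percentiles of the score. Leave readiness for change as its stages. Treat any subgroup table as a display, with its cuts fixed in advance.

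**MACRO-only route.** Model 3-month change by linear regression on the baseline characteristics. Keep the 2.60-point responder percentage as description. State that the results are predictors of improvement, not of treatment benefit.

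**Cost.** SAP wording only, with the same data and visits. The downsides are a functional-form check, plots or percentile estimates in place of a simple subgroup table, and some loss of power if the true moderation is a step at a cut.

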### Specific Aims/Hypotheses

**Aim 1:** To establish efficacy, safety and acceptability of the MACRO intervention via a RCT.

We hypothesize that after 3 months, compared to standard of care (SOC), participants randomized into the MACRO arm will have:

H1.1: Greater improvements in function as measured by Activity Measure for Post-Acute Care Computer Adaptive Test (AM-PAC-CAT) Basic Mobility Domain (primary outcome).

H1.2: Greater improvements in function as measured by accelerometry; AM-PAC CAT Daily Activity Domain; depression; frailty; self-efficacy; and quality of life. These will be collected to the extent possible in respect to local limitations that may result from fluctuations in COVID-19 prevalence.

H1.3: Greater CR participation and adherence.

H1.4: Greater impact in readmissions and hospitalization.

**Aim 2:** To examine the duration of benefit of MACRO compared to SOC.

H2.1: We hypothesize that relative MACRO benefits (i.e., function indices (see H1.2), adherence and readmissions/hospitalization will persist after 6 and 12 months (12 months will be captured as timing allows)

**Aim 3:** To explore characteristics of patients who benefit the most from the MACRO intervention.

H3.1: We anticipate functional capacity and other baseline characteristics will identify those who benefit from the MACRO intervention (exploratory).

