## Study Timeline

## 6.0 Study Endpoints

### 6.1 Primary and secondary study endpoints.

All eligible and consenting patients will undergo a standard battery of assessments at baseline and after approximately 3, 6, and 12 months (12 months as the study length allows). Assessors will be blinded regarding each patient's group assignment.

Aim 1: to test relative benefits of the MACRO vs. SOC arms, comparing (a) differences in the AM-PAC CAT Basic Mobility Domain (primary outcome; primary endpoint 3 months), as well as (b) complementary functional/qualitative metrics accelerometry, AM-PAC CAT Daily Activity Scale, depression, frailty, self-efficacy, and quality of life; (c) differences in participation, and adherence; (d) readmissions and hospitalization.

[figure not shown]
In Aim 2, assessments in physical activity (accelerometry); AM-PAC CAT Daily Activity Domain; depression; frailty; self-efficacy; and quality of life will be repeated at approximately 6 and 12 months (12 months as the study length allows) to evaluate longer term impact of the MACRO intervention vs. SOC.

In Aim 3, moderator analyses will examine characteristics of patients to identify those most likely to benefit from a MACRO intervention.

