**Aim 1 Analysis**-We will fit a series of linear mixed models using the SAS® MIXED procedure with baseline to follow-up changes in continuous outcomes as the dependent variable; intervention arm (MACRO/SOC), follow-up time point (3/6/12 months) and their interaction term as the fixed effects of interest; the baseline value of the continuous outcome as a fixed effect covariate; and a participant random effect to account for multiple measurements over time from the same participant. We will appropriately construct means contrasts to estimate MACRO vs SOC at each follow-up time point. The magnitude and statistical significance at  $\alpha=0.05$  of the MACRO vs SOC difference at 3 months for AM-PAC CAT Basic Mobility Domain will serve as the formal test of the primary hypothesis H1.1. If significant, we will define a meaningful responder as having at least a 2.60 point improvement in AM-PAC CAT Basic Mobility Domain over 3 months, compute percentage of responders in both arms, and conclude a number-needed-to-treat (NNT) as the reciprocal of the difference in percentages. We will employ the same analytic strategy described above for each of our secondary continuous outcomes such as physical activity, depression, frailty, self-efficacy and quality of life (H1.2). For the secondary outcomes measured only once at 3 months such as participation, adherence and satisfaction (H1.3), we will consider using Wilcoxon rank sum, chi-square and Fisher's exact tests to make between-intervention comparisons, depending on the categorical/ordinal/interval nature of the outcomes and their propensity for ill-behaved distributional properties. For count outcomes such as falls, number of medications, readmissions and hospitalizations in H1.4, we will fit a series of negative binomial regression models with the count outcome as the dependent variable; exposure time for the counts as an offset; a log link function; and intervention arm as the main independent factor of interest; and a marker of history of the outcome at baseline as a covariate MACRO vs SOC incident rate ratio and its statistical significance will serve as tests of H1.4.

**Aim 2 Analysis**-In the linear mixed models described above for H1.1 and H1.2, we will examine the between-intervention means contrasts at 6- and 12-months. The magnitude and statistical significance of the MACRO vs SOC arm differences at 6 and 12 months will serve as the formal test of the hypothesis H2.1.

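### Aim 3's MACRO-only responder model finds predictors of improvement, not predictors of benefit relative to SOC

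*Combined protocol and SAP*

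**What the plan says.** The question Aim 3 sets is comparative. Section 9.1 C (Aim 3 Analysis) opens: "We will examine characteristics of patients likely to reap the greatest benefits from MACRO compared to SOC arms". Section 6.1 says: "In Aim 3, moderator analyses will examine characteristics of patients to identify those most likely to benefit from a MACRO intervention". H3.1, under Specific Aims/Hypotheses, is likewise about who benefits from the intervention, and is labelled exploratory.

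Two avenues follow in section 9.1 C.

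- **First avenue, both arms.** "We will examine subgroups based on baseline AM-PAC CAT Basic Mobility Scale, frailty status, cognitive function, and readiness for change". Subgroup and subgroup-by-arm terms are added to the Aim 1 and Aim 2 models. Subgroup-specific comparisons are made only if the interaction is significant.
- **Second avenue, one arm.** "Specifically, we will only use the data from the MACRO arm, and define a meaningful responder as having a 3-month improvement"; the cut-off is a gain of 2.60 points or more on Basic Mobility. Responders and non-responders are compared at baseline. Univariable logistic models, a forward-selected multivariable model and possibly a classification tree follow. The product is called a "parsimonious collection of relevant baseline characteristics predictive of likelihood of benefit".

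The second avenue has no SOC comparison, no interaction step and no warning that its factors may be only prognostic. Section 9.1 D sizes it as follows: "assuming a half in the MACRO group responds, we would be able to fit a multivariable model with at least 15 variables".

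**The concern.** A participant's change in the MACRO arm is the change they would have had under SOC plus whatever MACRO added. With MACRO data alone the two parts cannot be separated. A factor that goes with faster recovery after a cardiac event, whatever the care, will predict response in the MACRO arm just as a true effect modifier would. More MACRO participants would not help.

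Taken at its word, the plan lets such factors be reported as identifying who benefits, which is the content of H3.1. For the four characteristics in the first avenue, a two-arm interaction is available to check this. For any other characteristic, the one-arm model is the only Aim 3 evidence. Section 7.2 collects several others at baseline, including depression, self-efficacy, activity status and aggregate risk, and section 9.1 D expects room for many variables.

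The second avenue also does not depend on MACRO working. In the Aim 1 Analysis, the step to "compute percentage of responders in both arms" is taken only if H1.1 is significant. The MACRO-only model has no such condition, so a trial with no effect at all could still yield factors described as predicting benefit.

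**Working it through.** **Inputs from section 9.1 D.** SD of change 7.97; difference 2.60; 149 completers per arm; two-sided alpha 0.05; half of the MACRO arm assumed to respond; 5 to 10 events per variable.

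**Step 1: the plan's own figures.** The SE of the arm difference is 7.97 × √(2/149) = 0.923. Then 2.60/0.923 = 2.816, and power = Φ(2.816 − 1.960) = Φ(0.856) = 80.4%, which agrees with the stated 80%. Responders in the MACRO arm: 149 × 0.5 = 74.5. That supports 14.9 variables at 5 events each and 7.45 at 10, so the stated 15 is reached only at the lenient end of the rule.

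**Step 2: how many responders would be expected without MACRO.** If change is normal and half of MACRO participants gain at least 2.60, the MACRO mean change is 2.60.

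- True effect 2.60: SOC mean 0, SOC response 1 − Φ(2.60/7.97) = 1 − Φ(0.326) = 37.2%. That is 0.372/0.50 = 74% of the MACRO rate.
- True effect 1.3: SOC response 43.5%, or 87% of the MACRO rate.
- No effect: SOC response 50%, the same as MACRO.

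Being a responder is therefore weak evidence of having benefited from MACRO.

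**Step 3: why the one-arm model cannot tell the two cases apart.** Take a binary factor.

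- Case A, prognostic only: it raises change by 2.6 points in both arms.
- Case B, true modifier: it does nothing under SOC and raises the MACRO effect by 2.6 points.

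In both cases the two factor groups in the MACRO arm differ by 2.6 points. The MACRO data can be identical, so any MACRO-only test flags both at the same rate.

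**Step 4: size, as an illustration.** Assumed, because the documents do not give them: a 50/50 factor, normal change, one univariable test at 0.05, and the shifts below.

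Hand check at a shift of 2.6, with the MACRO mean at the cut-off: response is Φ(1.3/7.97) = 0.565 against 0.435. The log odds ratio is 2 × ln(0.5648/0.4352) = 0.521. Its SE is √(2/(74.5 × 0.5648 × 0.4352)) = 0.330. The ratio is 1.58, and power is Φ(1.58 − 1.96) ≈ 35%.

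Simulation used 20,000 trials per scenario. The ranges cover three settings of (SOC mean change, MACRO effect): (0, 0), (0, 2.6) and (2, 2.6).

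| Equal shift in both arms (points) | Flagged by MACRO-only logistic model |
|---|---|
| 0 | 4.6–4.9% |
| 0.5 | 5.7–6.0% |
| 1.0 | 8.9–9.1% |
| 1.5 | 14.0–14.6% |
| 2.0 | 21.3–23.0% |
| 2.6 | 33.3–35.0% |
| 4.0 | 66.1–67.8% |
| 5.2 | 87.1–88.5% |

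In all these rows the two-arm interaction flags the factor at about the nominal rate: 4.8–5.6% on the responder scale and 4.7–5.2% on continuous change. A true modifier of 2.6 points with no SOC shift is flagged by the MACRO-only model in 33.4–34.8% of trials, which matches the 2.6 row as Step 3 predicts.

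**Step 5: what a two-arm interaction could detect.** With equal subgroups (74.5 per cell), SE = 7.97 × √(4/74.5) = 1.847.

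| Difference in effect (points) | Power, continuous change | Power, responder logistic (simulated) |
|---|---|---|
| 2.60 | 29% | 19–21% |
| 4.0 | 58% | 39–42% |
| 5.2 | 80% | 59–61% |

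**The case against.** The best defence has four parts.

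- **Exploratory status.** H3.1 and both avenues are labelled exploratory, and no confirmatory test rests on them. This stands and limits the importance of the point. But the label warns about strength of evidence and multiplicity; it does not turn a one-arm association into effect modification.
- **The first avenue already answers the moderator question,** for baseline mobility, frailty, cognition and readiness for change. This also stands, and it covers the characteristic most open to regression to the mean, the baseline mobility score. The gap is confined to characteristics outside the four.
- **Benefit may just mean responding.** The comparison with SOC appears in the sentence that introduces the subgroup analyses, and the second avenue states its outcome and its data openly. Read that way, the model answers a legitimate one-arm question. But the same section uses the word benefit for MACRO against SOC, and section 6.1 describes the whole of Aim 3 as moderator analysis. If improvement is meant, the text should say so.
- **The magnitudes rest on assumed shifts.** True. At 0.5 to 1.5 points the flag rate is only about 6% to 14%. The highest rates need shifts of 4.0 to 5.2 points, which is 1.5 to 2 times the plan's important difference. These are also rates of detecting a real association; the error lies in the label then put on it. The argument in Step 3 needs none of these values.

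The low power in Step 5 is a fair objection to insisting on more interaction tests. It is no reason to put a one-arm analysis in their place.

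**Conclusion.** The concern holds. As written, the second avenue attributes to MACRO any factor that predicts improvement, and no SOC comparison or caveat prevents this. That conclusion follows from the design and needs no numerical assumption.

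Its size depends on how strongly the candidate factors predict recovery, which the documents do not say. Under the assumptions in Step 4, a prognostic-only factor is flagged in about 6% of trials at a 0.5-point shift, 34% at 2.6 points and 88% at 5.2 points, against about 5% for a two-arm interaction.

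This is a fault of interpretation in an exploratory aim. The primary test and the sample size are not affected. It should be corrected because results on who benefits could guide who is offered the programme, and the correction costs almost nothing.

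**What to change.** **Main change, in section 9.1 C, Aim 3 Analysis.** Describe the MACRO-only output as predictors of improvement among MACRO participants. Remove the two statements that these factors show who is likely to benefit: the sentence introducing the second avenue, and the phrase "parsimonious collection of relevant baseline characteristics predictive of likelihood of benefit". Add that conclusions on H3.1 rest on the two-arm interactions only. This is one paragraph of wording, with no new data or analysis.

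**Optional.** For any further characteristic that is to be claimed as predicting benefit, fit characteristic-by-arm terms in both arms, preferably on the continuous change score as in the first avenue. For any tree, report the MACRO-minus-SOC difference in each terminal group. The SOC change scores are already collected. The cost is low power (Step 5) and more tests, so few factors would be flagged and the report should say so.

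If a two-arm responder model is chosen instead, restate the variable count in section 9.1 D. With 50% response under MACRO and an assumed 30% to 50% under SOC, there would be 119 to 149 responders (74.5 + 149 × 0.3 = 119.2; 74.5 + 149 × 0.5 = 149). With one arm term and two terms per characteristic, the number of characteristics is (responders ÷ events per variable − 1) ÷ 2. That gives 11 to 14 characteristics at 5 events per variable and 5 to 6 at 10.

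### The exploratory Aim 3 responder model selects its predictors on one set of MACRO-arm data without internal validation, so they will be unstable and any performance figure optimistic

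*Combined protocol and SAP*

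**What the plan says.** Section 9.1 C, Aim 3 Analysis, has two parts. The first tests subgroup-by-arm interactions for four named baseline features. The second, at issue here, looks for characteristics of patients who do well: "we will only use the data from the MACRO arm". The plan will "define a meaningful responder as having a 3-month improvement of at least 2.60 points in AM-PAC CAT Basic Mobility Scale". It then compares responders with non-responders at baseline, fits a separate logistic model for each characteristic, and builds a multivariable model with "a forward selection strategy to potentially identify a parsimonious collection of relevant baseline characteristics predictive of likelihood of benefit". Finally, to allow for non-linearity and interactions, "we will consider a classification tree model or CART".

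Section 9.1 D supports the size of this model: "assuming a half in the MACRO group responds, we would be able to fit a multivariable model with at least 15 variables". It bases this on 5 to 10 events per variable.

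Sections 9.1 C and 9.1 D give no candidate list, screening or entry threshold, pruning rule, hold-out sample, cross-validation, bootstrap or shrinkage for this model. The sensitivity analyses (added covariates, missing data, zero-inflated or dichotomous models, transformation) do not deal with selection. H3.1 is labelled exploratory.

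**The concern.** Screening, forward selection and tree growing all search the data for the strongest associations, and here the same data would also supply the description of what was found. A characteristic that looks strong by chance is more likely to be selected, so selected effects and fit are biased upward. With no record of how often each characteristic would be selected on resampling, a reader cannot tell a stable finding from a chance one.

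What is at stake is the description of which patients do well with MACRO, and hence which characteristics later work takes up. The primary and secondary comparisons are not affected.

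**Working it through.** **Inputs from the plan.** 187 randomized per arm, with 149 expected to complete ("We plan to randomize 187+187=374 participants, anticipating 149+149 completers assuming a conservative 80% retention rate"); half of the MACRO arm responding; 5 to 10 events per variable.

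**Inputs assumed, because the plan gives none.** 15, 20 or 30 continuous candidates; screening at p<0.05 to 0.20; entry at p<0.05, or 0.10 as a looser case. The range of candidates is reasonable: Table 1 and section 7.2 describe about 16 baseline measures (two AM-PAC domains, accelerometry, Short Blessed, PHQ-9, readiness for change, self-efficacy, RAND-12, falls, deprescribing-eligible medications, DASI, FRAIL, REALM-SF, REAP-S, food record, risk assessment), before age, diagnosis and site.

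**1. The plan's own figures.** With SD 7.97 and a difference of 2.60, n per arm = 2 × (1.96 + 0.84)² × 7.97² / 2.60² ≈ 148, or 149 with the t-distribution. 187 × 0.80 = 149.6. Both agree with the plan. For the responder model, 149 × 0.5 = 74.5 events; 74.5 / 5 = 14.9 variables and 74.5 / 10 = 7.45. So 15 is the ceiling at the loosest end of the plan's rule, not a floor. The count also covers only the fitted model, whereas selection searches every candidate: 74.5 / 20 = 3.7 events per candidate with 20, and 74.5 / 30 = 2.5 with 30.

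**2. No true predictor, by formula.** For k independent candidates and entry at p<0.05, P(at least one selected) ≈ 1 − 0.95^k: 54% for k = 15, 64% for 20, 79% for 30. Sample size does not enter.

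**3. No true predictor, by simulation** (149 participants, half responding, 400 replicates, so a Monte Carlo standard error of at most √(0.25/400) = 2.5 percentage points):
- Entry at p<0.05: at least one selected in 53–56% (15 candidates), 66–67% (20) and 79–81% (30).
- 20 candidates correlated at 0.3: 52–53%.
- Screen p<0.20, entry p<0.10: 78%, 90% and 97% for 15, 20 and 30 candidates.
- When a model is selected, mean apparent AUC is 0.62–0.67; in new data it is 0.50.

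**4. Three true predictors** (screen p<0.20, entry p<0.05):

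| Log-odds per SD | Candidates | True selected | Noise selected | Noise share | Apparent AUC | New-data AUC | Gap |
|---|---|---|---|---|---|---|---|
| 0.3 | 20 | 1.27 | 0.89 | 0.89/2.16 = 41% | 0.676 | 0.574 | 0.10 |
| 0.3 | 30 | 1.21 | 1.58 | 1.58/2.79 = 57% | 0.693 | 0.562 | 0.13 |
| 0.5 | 20 | 2.385 | 0.815 | 0.815/3.20 = 25% | 0.740 | 0.672 | 0.07 |
| 0.5 | 30 | 2.37 | 1.50 | 1.50/3.87 = 39% | 0.752 | 0.658 | 0.09 |

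**5. Tree (depth 2 or 3, 15–30 candidates).** With no signal, apparent AUC is 0.69–0.78 against 0.50 in new data. With three predictors at 0.5 per SD, it is 0.73–0.82 against 0.57–0.59.

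**The case against.** A reader might infer that the model's findings will be largely chance. The documents do not support that. It is so if nothing predicts response, but complete absence of signal is unlikely: the outcome is a dichotomised change score, and baseline mobility is a natural candidate. With three predictors at 0.5 per SD, 61–75% of selections are real. At 0.3 per SD the split is nearer even (43–59% real).

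A reader might also infer that the plan commits to reporting an inflated accuracy. It does not: no AUC, calibration or classification measure is mentioned, the wording is tentative, and the tree is only to be considered. The AUC results therefore apply only if performance is reported. Instability of selection applies either way.

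The exploratory label is a fair defence against a graver charge, since no primary or secondary conclusion rests on this model. It does not supply the missing information on which selections would recur.

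The candidate count and cut-offs are assumptions, and correlated candidates lower the false-selection rate (66% to about 53% with 20 candidates). If imputed data for all 187 MACRO participants were used, events would rise to 187 × 0.5 = 93.5, but the chance of selecting something when nothing matters would hardly change, because it depends on the number of candidates and the cut-off. Imputation would not provide validation either.

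**Conclusion.** The point holds as a low-priority, inexpensive improvement to an exploratory analysis. Following the stated procedure gives unstable predictors and, where performance is reported, optimistic figures. If nothing matters, at least one predictor is still selected in about 52–81% of trials at entry p<0.05, and in up to about 97% with looser cut-offs. If three predictors matter, roughly 25–40% of selections are noise at 0.5 per SD; at 0.3 per SD the share is about 40% with 20 candidates and higher with 30. AUC is overstated by about 0.07–0.09 and 0.10–0.13 respectively. These sizes rest on the assumed 15–30 candidates, thresholds and effect sizes, and on the plan's 149 completers with half responding. The direction does not depend on the exact values.

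Validation would not let the model show who benefits from MACRO relative to SOC. A single-arm model identifies who improves; relative benefit is the subject of the separate interaction analysis.

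**What to change.** Add to section 9.1 C, Aim 3 Analysis:
- A list of candidate characteristics, the screening and entry thresholds, and the stopping or pruning rule for any tree.
- Whether the model uses completers or imputed data.
- Repetition of the whole procedure (screening, forward selection and any tree) in at least 500 bootstrap samples, within each imputed dataset if imputation is used. With the plan's five imputations that is 5 × 500 = 2,500 runs.
- The selection frequency of each characteristic and, if any performance measure is reported, its optimism-corrected value (AUC and calibration slope).
- A statement that the result is hypothesis-generating and describes improvement within the MACRO arm.

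The cost is a short addition to the text and some computing, with slightly more programming if imputed datasets are used. No new data are needed and the primary analysis is unchanged. The downside is that results will look less favourable.
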